10.20.2 Management of diarrhea

Severe (Grade 3) diarrhea is defined as an increase of ≥ 7 stools per day or hospitalization for management of diarrhea or limiting self-care ADL. Determination of the severity of diarrhea will be consistent with CTCAE version 5.0 (Section 10.3).

Diarrhea will be treated as clinically indicated according to the local guidelines.

Stool samples may be collected for stool analysis to rule out infection for study participants reporting severe diarrhea. Stool sampling will be as clinically indicated in the opinion of the Investigator and assessed per local guidance. In addition, collection of blood samples for assessment of exploratory safety biomarkers is required for study participants with severe GI disturbances including diarrhea.

PUBLIC COPY
This document cannot be used to support any marketing authorization application and any extensions or variations thereof.

10.20.3 Management of infections and hypogammaglobulinemia

Study participants who have signs or symptoms of any infection should be monitored closely and managed according to local guidelines. This may include tests for specific organisms if clinically indicated.

Study participants **MUST discontinue IMP AND move** into **the SFU Period** if any of the following events occur: Study participant has a serious infective episode requiring hospitalization or IV antibiotic therapy (ie, bacteremia or sepsis, bacterial meningitis, osteomyelitis or septic arthritis, bacterial pneumonia, or visceral abscess).

To maintain the study integrity, IgG level will remain blinded to the study sites and the UCB study team for the first 4 weeks of the study. To ensure patient safety, serum IgG level will be monitored by an independent medical monitor external to UCB including signs and symptoms of infection and associated laboratory parameters. The IMP may be temporarily discontinued as requested by the independent medical monitor when deemed appropriate.

In the event of a non-serious infection, the Benefit-Risk of continuing treatment with IMP must be carefully evaluated by the Investigator in collaboration with the medical monitor. Treatment may be temporarily discontinued for the study participant who develops a non-serious persisting or recurrent infection with a serum total IgG level between $\geq 1\text{g/L}$ and $< 2\text{g/L}$. Upon resolution of infection and the IgGs returning to the level of $\geq 2\text{g/L}$, the study participant may be allowed to resume treatment with the IMP. Ad hoc assessment can be performed to monitor the recovery of IgG levels.

Treatment **MUST** be temporarily discontinued for the study participant who develops an event of hypogammaglobulinemia with a serum total IgG of $< 1\text{g/L}$ irrespective of infection. When the IgG level reaches $\geq 2\text{g/L}$, the study participant may be allowed to continue treatment with IMP.

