7.1.3 Discontinuation of study medication due to other AEs or medical conditions

A study participant **must** permanently discontinue study medication if any of the following events occur:

1. Study participant develops an illness that would interfere with his or her continued participation.
2. Study participant has new onset or recurrent neoplastic disease (except for superficial basal or squamous cell carcinoma of the skin not requiring targeted biological therapy, chemotherapy or radiation)
3. Study participant has a serious infective episode requiring hospitalization or IV antibiotic therapy (including but not limited to bacteremia or sepsis, meningitis, osteomyelitis or septic arthritis, pneumonia, or visceral abscess).
4. Study participant meets potential drug-induced liver injury (PDILI) permanent discontinuation criteria.
5. Study participant has a TB test that is confirmed positive or any further evidence suggestive of potential TB infection (ie, exposure) and further examinations result in a diagnosis of active TB or latent TB infection (LTBI).
6. If a nontuberculosis mycobacterium infection (NTMB) is identified during a study, the same withdrawal procedures as those used for an active TB infection identified during the study should be followed.
7. Study participant experiences a serious AE of headache which is considered related to the study medication in the opinion of the Investigator.
8. Study participant has an AE of severe or serious infusion or anaphylactic reaction requiring corticosteroid and/or epinephrine therapy (see Section 10.22) (Sampson et al, 2006).

Study participants **may** permanently discontinue study medication at the discretion of the Investigator, Medical Monitor, and Study Physician if any of the following events occur:

9. Study participant is noncompliant with the study procedures or medications in the opinion of the Investigator.
10. Study participant takes prohibited concomitant medications as defined in this protocol.

Investigators should contact the Medical Monitor, whenever possible, to discuss the withdrawal of a participant in advance. Investigators should attempt to obtain information on study participants in the event of withdrawal (eg, reason for withdrawal, any safety information).

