7.1.4 Temporary IMP discontinuation

Study participant ***must be*** TEMPORARILY discontinued from the IMP if any of the following events occur:

1. The study participant develops an event of hypogammaglobulinemia with a serum total IgG of <1g/L irrespective of infection. When the IgG level reaches ≥ 2 g/L, the study participant may be allowed to continue treatment with IMP (see Appendix 22; Section 10.22.3).
2. In the event of confirmed COVID-19 infection. IMP may be restarted if clinically appropriate when signs and symptoms have resolved.

Study participants ***may be TEMPORARILY discontinued from the IMP*** if the following events occur:

1. The study participant develops a non-serious persisting or recurrent infection with serum total IgG level between ≥ 1 and <2g/L. Upon resolution of infection and the IgG returning to level of ≥ 2 g/L, the study participant may be allowed to resume treatment with the IMP (see Appendix 22; Section 10.22.3).
2. In the event of suspected (eg, signs/symptoms such as fever, cough, shortness of breath) COVID-19 infection, or known exposure sufficient to necessitate testing or self-imposed quarantine, IMP may be restarted when clinically appropriate if:
 - a. COVID-19 test is negative, and signs and symptoms have resolved.
 - b. If test is not available, resolution of signs and symptoms and 14 days have passed since initial presentation of the clinical signs/symptoms.
 - c. If asymptomatic, 14 days have passed since known exposure.

The investigator should discuss with sponsor's study physician prior to re-initiating the IMP. As appropriate, virtual assessments could continue (eg, AE collection, PRO assessments).

If IMP treatment is resumed, continue the next dose as previously scheduled. No "make up" dose is permitted. The participant should subsequently follow the visit schedule as described in the protocol and the eCRF should be completed accordingly.

The study participant should follow the visit schedule as described in the protocol and the eCRF completed accordingly.

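### Protocol 7.1.3 and 7.1.4 give different outcomes for a participant hospitalised with confirmed COVID-19, and the serious-infection list in 10.20.3 is narrower than the one in 7.1.3

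*Protocol*

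**What the plan says.** **Protocol 7.1.3** lists events after which a participant must "permanently discontinue study medication if any of the following events occur". Criterion 3 is: "Study participant has a serious infective episode requiring hospitalization or IV antibiotic therapy". The bracketed examples that follow are open-ended: "including but not limited to bacteremia or sepsis, meningitis, osteomyelitis or septic arthritis, pneumonia, or visceral abscess". Meningitis and pneumonia carry no restriction on organism.

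**Protocol 7.1.4** lists events after which a participant must be "TEMPORARILY discontinued from the IMP if any of the following events occur". The second is: "In the event of confirmed COVID-19 infection. IMP may be restarted if clinically appropriate when signs and symptoms have resolved". The investigator should speak to the sponsor's study physician before restarting, and the participant stays on the visit schedule. Nothing separates mild from serious or hospitalised COVID-19, and nothing points back to 7.1.3.

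**Protocol 10.20.3**, to which 8.3.7 sends investigators for infection management, uses the same trigger as 7.1.3 criterion 3 and requires the drug to be discontinued. Its examples are introduced by *ie* and are narrower: "ie, bacteremia or sepsis, bacterial meningitis, osteomyelitis or septic arthritis, bacterial pneumonia, or visceral abscess". The participant then moves into an SFU Period. The section's hold rule for infection is confined to non-serious cases with IgG from 1 to below 2 g/L: "Treatment may be temporarily discontinued for the study participant who develops a non-serious persisting or recurrent infection".

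**Protocol 7.2** sends participants who discontinue study medication during treatment to a PEOT visit and then the Observation Period.

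**SAP 2.2.1.1** (as Protocol Section 3) makes TEAEs that lead to permanent withdrawal of study drug a primary safety endpoint. **SAP 8.2.2** tabulates permanent and temporary withdrawals separately.

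**The concern.** A stopping rule should give the same answer whichever section the site opens. Here a participant hospitalised with confirmed COVID-19 meets a mandatory permanent stop in one section and a mandatory hold with optional restart in the next. For hospitalised meningitis or pneumonia of viral origin, the body of the protocol and its management appendix define the mandatory stop differently.

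Three things are at stake. The first is handling: Protocol 2.3 names infection as a potential risk of this drug, and the sections differ on whether re-exposure is possible after a serious one. The second is follow-up: a permanent stop leads to PEOT and the Observation Period, while a hold keeps the participant on the regular schedule. The third is a primary endpoint: whether the event counts as permanent or temporary withdrawal may depend on the section the site applied. Classification can also matter for the COVID-19-free MG-ADL summary in SAP 9.1.1, which excludes participants who discontinue treatment because of COVID-19.

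**Working it through.** The plan states no figure to reproduce. The check is a comparison of the current text, followed by one illustrative division.

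**Step 1. Apply each section to each case.**

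| Participant | 7.1.3 criterion 3 | 7.1.4 | 10.20.3 |
|---|---|---|---|
| Hospitalised, confirmed COVID-19 pneumonia | Mandatory permanent stop | Mandatory hold, restart allowed | Not listed unless it also presents as a listed condition such as sepsis; too serious for the infection hold |
| Hospitalised viral meningitis or pneumonia, not COVID-19 | Mandatory permanent stop | No rule specific to it | Not listed; too serious for the infection hold |
| Hospitalised sepsis, osteomyelitis, septic arthritis or visceral abscess, any organism | Mandatory permanent stop | No rule specific to it | Mandatory stop |
| Non-serious persisting or recurrent infection, IgG 1 to below 2 g/L | Not triggered | Optional hold | Optional hold |

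The separate IgG rule (below 1 g/L, irrespective of infection) is the same in 7.1.4 and 10.20.3 and does not affect the comparison. 10.20.3 also lets the independent medical monitor request a hold, but does not tie this to serious viral infection.

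Row 1 is a permanent-versus-temporary conflict between 7.1.3 and 7.1.4. Row 2 is a difference in scope between 7.1.3 and 10.20.3. Rows 3 and 4 agree.

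**Step 2. Look for text that settles row 1.** Protocol 6.6 points to Section 7.1 for the discontinuation criteria, but 7.1.3 and 7.1.4 both sit within 7.1, so this does not rank them. Protocol 8 allows no waivers or exemptions, so a site that restarts under 7.1.4 after a hospitalised infection may be departing from 7.1.3.

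**Step 3. Check the pointers.** The SFU Period is not defined in the protocol or in its abbreviation list; the study periods are Treatment and Observation. For low IgG and infection, 7.1.4 cites Appendix 22, Section 10.22.3. Appendix 22 is now the anaphylaxis criteria questionnaire, and the infection guidance is in Section 10.20.3.

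**Step 4. Size per participant.** Inputs: maximum sample size 240 (SAP 3.9) and 1:1 randomisation (Protocol 4.1), so 240 / 2 = 120 per arm.

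- Overall: 1 / 240 = 0.42%, about 0.4 percentage points per reclassified participant.
- One arm: 1 / 120 = 0.83%, about 0.8 points.
- If 1 to 5 participants were affected (an assumption): 0.4 to 2.1 points overall (5 / 240 = 2.08%), or 0.8 to 4.2 points if all were in one arm (5 / 120 = 4.17%).

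A smaller enrolled number makes each shift larger. SAP 8.2.2 groups TEAEs by most recent dose, so with dose switching the group denominators will not be exactly 120.

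**The case against.** The strongest reply is that 7.1.3 and 7.1.4 can both be obeyed. Restart under 7.1.4 is a permission, conditional on clinical judgement and discussion with the study physician. A site that never restarts a hospitalised participant breaches neither section. That is correct, and it shows that the two rules are not strictly incompatible. It does not show that sites will read them together: a site working from 7.1.4 alone may restart, and nothing there warns that 7.1.3 may already have closed that option.

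It can also be said that the 10.20.3 list is probably wording left unharmonised when criterion 3 of 7.1.3 was updated, that SFU is a labelling slip, and that 7.2 already fixes the follow-up. These explanations are plausible, but they are inferences and the text should not need them.

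On consequences, the endpoint counts what sites actually did, all analyses are descriptive (SAP 4.1 and 4.6), and serious TEAEs, temporary withdrawals and infections are tabulated elsewhere. All of this stands: no inference changes and the infection signal is not lost.

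A reader might infer something wider, namely that all three sections disagree on permanent stop versus temporary hold for any hospitalised viral infection, or that every hospitalised non-bacterial infection is affected. The documents support neither. No section prescribes a temporary hold because of a hospitalised viral infection other than COVID-19; 10.20.3 simply leaves viral meningitis and pneumonia off its list. In that list only meningitis and pneumonia are limited to bacterial causes, so the remaining conditions are covered alike in both sections.

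**Conclusion.** The point holds in two bounded parts. First, for hospitalised confirmed COVID-19, 7.1.3 requires a permanent stop while 7.1.4 requires a hold and permits restart, with no exception, cross-reference or stated precedence. Second, 7.1.3 and 10.20.3 attach different lists to the same trigger, so hospitalised viral meningitis or pneumonia is a mandatory stop in one and unlisted in the other. The undefined period name and the outdated cross-reference are minor, but they are in the same passages.

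The effect on the primary endpoint is small per case and its total cannot be estimated, because the documents give no rate of hospitalised viral infection. The per-participant shifts rest on the SAP maximum of 240, equal arms, and a case actually being handled differently because of the wording. The textual conflict depends on none of these. It should be corrected because it concerns a mandatory safety rule and feeds a primary safety endpoint.

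**What to change.** Reconcile Protocol 7.1.3, 7.1.4 and 10.20.3 so that they give:

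- one rule for hospitalised confirmed COVID-19, with the precedence between 7.1.3 and 7.1.4 stated and each section referring to the other;
- one common list of serious infections in 7.1.3 and 10.20.3, making clear whether it is open or closed and whether meningitis and pneumonia are limited to bacterial causes;
- one name for the follow-up period, matching 7.2;
- a corrected reference in 7.1.4 to the infection guidance in 10.20.3.

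Which clinical rule applies is for the sponsor to decide; this review takes no position on it. The cost is protocol wording and notice to sites. No assessment, data collection or SAP table has to change. If cases have already occurred, the study report could list participants hospitalised with COVID-19 or with viral meningitis or pneumonia, showing the action taken with study drug, so that readers can see how each was counted.

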10.20.4 Management of infusion reactions or hypersensitivity reactions

Study participants must be closely monitored for reactions during and after the study treatment administration period. Standard precautions must be taken for the study participants with regard to SC infusion complications. Suggested management guidelines for infusion-related reactions and anaphylaxis at the study site are provided in [Table 10-4](#). Definitions of mild, moderate, and severe events will be consistent with CTCAE version 5.0 (Section 10.3). Nurses administering the IMP at home should follow their own management guidelines, which should be reviewed and endorsed by the Investigator prior to first home administration.

Table 10-4: Suggested management guidelines for infusion reactions or anaphylaxis

Type of reaction	Suggested action
Acute – Mild Grade 1	Monitor vital signs every 10 min. If the reaction worsens to Grade 2, follow the instruction below.
Acute – Moderate Grade 2	Interrupt/hold infusion temporarily to further assess and initiate treatment if necessary. Consider the use of IV fluid and antihistamine IV/IM. Consider administering paracetamol or NSAIDs. Monitor vital signs initially every 5 min. If the reaction improves and upon further assessment it is clear that the event is not an anaphylaxis, restart the infusion cautiously. Continue monitor vital signs every 5 minutes. If reaction recurs or worsens to Grade 3, discontinue infusion.
Acute – Severe Grade 3 or anaphylaxis	Discontinue IMP infusion permanently. Alert crash team. Maintain airway; ensure oxygen is available. Administer: 
 – Antihistamine IV/IM, corticosteroids IV, epinephrine IM, and IV fluids as appropriate. – Monitor vital signs every 2 min. – Hospitalize, if condition not improving or worsens – Monitor patient until symptoms resolve.

CTCAE=Common Terminology Criteria for Adverse Events; IM=intramuscular; IMP=investigational medicinal product; IV=intravenous(ly); NSAID=nonsteroidal anti-inflammatory drug

Note: Management criteria were adapted from the CTCAE v5.0 (National Cancer Institute, 2017).

[figure not shown]
Conditions in which anaphylaxis is likely should be diagnosed using Sampson’s Criteria (Sampson et al, 2006) as described in (Appendix 22, Section 10.22). The infusion must be discontinued immediately, and emergency resuscitation measures implemented.

[figure not shown]
If an infusion-related reaction or anaphylaxis occurs, a blood sample will be collected from the study participant as soon as possible, while the event is ongoing, to investigate the nature of the reaction as per Schedule of Activities (Section 1.3).

[figure not shown]
Samples for serum complement (C3, C4), serum cytokines, and plasma complement (C3a, C5a) should be collected as specified in the Schedule of Activities (Section 1.3). Additional tests such as IgE levels, tryptase may be performed when there is a suspicion of Type I or III hypersensitivity reaction. The results of all monitoring, including laboratory testing, should be made available to the study site and Sponsor.

PUBLIC COPY
This document cannot be used to support any marketing authorization application and any extensions or variations thereof.

10.21 Appendix 21: Headache questionnaire

10.22 Appendix 22: Sampson Criteria Questionnaire

Anaphylaxis is highly likely when any of the following 3 criteria is fulfilled ([Sampson et al, 2006](#)):

[figure not shown]
1. Acute onset of an illness (minutes to several hours) with involvement of the skin, mucosal tissue, or both (eg, generalized hives, pruritus or flushing, swollen lips-tongue-uvula)

[figure not shown]
AND AT LEAST ONE OF THE FOLLOWING

- d. Respiratory compromise (eg, dyspnea, wheeze-bronchospasm, stridor, reduced peak expiratory flow [PEF], hypoxemia)
 - e. Reduced BP or associated symptoms of end-organ dysfunction (eg, hypotonia [collapse], syncope, incontinence)
2. Two or more of the following that occur rapidly after exposure to a likely allergen for that patient (minutes to several hours):
 - a. Involvement of the skin-mucosal tissue (eg, generalized hives, itch-flush, swollen lips tongue-uvula)
 - b. Respiratory compromise (eg, dyspnea, wheeze-bronchospasm, stridor, reduced PEF, hypoxemia)
 - c. Reduced BP or associated symptoms (eg, hypotonia [collapse], syncope, incontinence)
 - d. Persistent GI symptoms (eg, crampy abdominal pain, vomiting)

Reduced BP after exposure to known allergen for that subject (minutes to several hours):
Systolic BP of less than 90mmHg or greater than 30% decrease from the subject's Baseline systolic BP value.

[figure not shown]
10.23 Appendix 23: Columbia-Suicide Severity Rating Scale

[figure not shown]
This

tion

This

ation

This

on

ICH	International Council for Harmonisation
IDMC	Independent Data Monitoring Committee
IEC	Independent Ethics Committee
IGRA	Interferon Gamma Release Assay
IMP	Investigational Medicinal Product
INR	International Normalized Ratio
IRB	Institutional Review Board
IVIg	Intravenous Infusion of Immunoglobulin G
LDH	Lactate Dehydrogenase
LLOQ	Lower Limit of Quantification

MA	Markedly Abnormal
MedDRA	Medical Dictionary for Regulatory Activities
MG	Myasthenia Gravis
MG-ADL	MG-Activities of Daily Living
MG-C	MG-Composite
MGII	MG Impairment Index
MGQoL15r	Revised 15-item MG Quality of Life
MRD	Minimum Required Dilution
NAb	Neutralizing Antibody
PDILI	Potential Drug-Induced Liver Injury
PEOT	Premature End of Treatment
PEX	Plasma Exchange
PK	Pharmacokinetic
PRO	Patient-Reported Outcome
PT	Preferred Term
PTT	Partial Prothrombin Time
QMG	Quantitative Myasthenia Gravis
RBC	Red Blood Cell
RLZ	Rozanolixizumab
RS	Randomized Set
SAP	Statistical Analysis Plan
sc	Subcutaneous
SD	Standard Deviation
SDR	Safety Data Review
SGPT	Serum Glutamic-Pyruvic Transaminase
SOC	System Organ Class
SS	Safety Set
TB	Tuberculosis
TEAEs	Treatment-Emergent Adverse Events
TFLs	Tables, Figures and Listings
ULN	Upper Limit of Normal
VAS	Visual Analogue Scale
WBC	White Blood Cell
WHODD	World Health Organization Drug Dictionary

1 INTRODUCTION

The purpose of this statistical analysis plan (SAP) is to provide all information that is necessary to perform the statistical analyses of study MG0004, including independent Data Monitoring Committee (IDMC) and final analyses. It also defines the summary tables, figures and listings (TFLs) to be included in the final Clinical Study Report (CSR) according to the protocol.

This SAP is based upon, and assumes familiarity with, the following documents:

- Protocol Amendment 2: 30 July 2020
- IDMC Charter v1.0: 31 March 2020

If a future protocol amendment necessitates a substantial change to the statistical analysis of the study data, this SAP may be amended accordingly. Changes to the analysis from the protocol are documented in [Section 3.9](#). The content of this SAP is compatible with the International Council for Harmonisation (ICH)/Food and Drug Administration (FDA) E9 Guidance documents.

2 PROTOCOL SUMMARY

2.1 Study objectives

2.1.1 Primary objective

To evaluate the long-term safety and tolerability of rozanolixizumab in study participants with generalized myasthenia gravis (MG)

2.1.2 Secondary objective

To evaluate the long-term efficacy of rozanolixizumab in study participants with generalized MG

